## 1 PROTOCOL SUMMARY

Title:	A Prospective, Multi-Center, Randomized, Concurrently-Controlled Clinical Study of the BARD® COVERA™ Arteriovenous (AV) Stent Graft in the Treatment of Stenosis in the Venous Outflow of AV Fistula Access Circuits																																													
Sponsor:	Bard Peripheral Vascular, Inc. [name]																																													
Objective :	The objective of this study is to assess the safety and effectiveness of the COVERA™ Vascular Covered Stent for the treatment of stenotic lesions in the upper extremity venous outflow of the AV access circuit.																																													
Design & Overview:	
This is a prospective, multi-center, randomized, concurrently-controlled clinical study designed to assess the safety and effectiveness of the COVERA™ Vascular Covered Stent for the treatment of stenotic lesions in the upper extremity venous outflow of the AV access circuit of hemodialysis subjects dialyzing with an AV fistula. This study will compare the use of the COVERA™ Vascular Covered Stent (following percutaneous transluminal angioplasty (PTA)) to PTA alone. This treatment is called the “Index Procedure.”
 
Follow-up for all treated subjects will be performed at hospital discharge, 30 and 90 days, as well as 6, 12, 18, and 24 months post-index procedure.
																																													
Study Device:	
The COVERA™ Vascular Covered Stent is a highly flexible self-expanding endoprosthesis comprised of expanded polytetrafluoroethylene (ePTFE) encapsulating a nitinol (nickel-titanium alloy) stent framework. The inner lumen of the stent graft (blood contacting surface) is carbon impregnated.
 
The COVERA™ Vascular Covered Stent is available in a straight and a flared configuration. Devices will come on either an 8F or 9F system.
 
Table 1: COVERA™ Vascular Covered Stent Sizes
 
  
 	Covered Stent Length (mm)	Endovascular System Length (cm)	
 
 30*	40	60	80	100	
   
 Covered Stent Outer Diameter (mm)	6	✓	✓	✓	✓	✓	80 and 120	
 
 7	✓	✓	✓	✓	✓	
 
 8	✓	✓	✓	✓	✓	
 
 9	✓	✓	✓	✓	✓	
 
 10	✓	✓	✓	✓	✓	
  
 
* Note: only the straight configuration of the implant is available in 30mm length.
			Covered Stent Length (mm)					Endovascular System Length (cm)	30*	40	60	80	100	Covered Stent Outer Diameter (mm)	6	✓	✓	✓	✓	✓	80 and 120	7	✓	✓	✓	✓	✓	8	✓	✓	✓	✓	✓	9	✓	✓	✓	✓	✓	10	✓	✓	✓	✓	✓
				Covered Stent Length (mm)						Endovascular System Length (cm)																																				
		30*	40	60	80	100																																								
Covered Stent Outer Diameter (mm)	6	✓	✓	✓	✓	✓	80 and 120																																							
	7	✓	✓	✓	✓	✓																																								
	8	✓	✓	✓	✓	✓																																								
	9	✓	✓	✓	✓	✓																																								
	10	✓	✓	✓	✓	✓																																								

Enrollment:	A total of 280 subjects will be randomized to the study. The primary endpoint analysis will occur when 280 randomized subjects have completed or discontinued before their 6 month follow up. The key secondary endpoint analysis will occur when 280 randomized subjects have completed or discontinued before their 12 month follow up. All subjects will be followed for 24 months post index-procedure.
Investigational Sites:	Up to 35 investigational sites in the United States (US), Europe, and Australia/New Zealand will participate. Treated subjects will be distributed globally with 50-75% of the treated subjects in the U.S.
Study Population:	Male or non-pregnant female $\geq 21$ years of age with an expected lifespan sufficient to allow for completion of all study procedures. Eligible subjects will have a hemodynamically significant stenosis.
Inclusion Criteria	
Clinical Inclusion Criteria
 
 
1. Subject must voluntarily sign and date the Informed Consent Form (ICF) prior to collection of study data or performance of study procedures.
 
2. Subject must be either a male or non-pregnant female <math>\geq 21</math> years of age with an expected lifespan sufficient to allow for completion of all study procedures.
 
3. Subject must be willing to comply with the protocol requirements, including clinical and telephone follow-up.
 
4. Subject must have an upper extremity AV fistula that has undergone at least one successful dialysis session with two-needle cannulation, prior to the index procedure.
 
 
Angiographic Inclusion Criteria
 
 
5. Subject must have angiographic evidence of a stenosis <math>\geq 50\%</math> (by visual estimation) located in the venous outflow of the AV access circuit and present with clinical or hemodynamic evidence of AV fistula dysfunction.
 
6. The target lesion must be <math>\leq 9</math>cm in length. Note: multiple stenoses may exist within the target lesion.
 
7. The reference vessel diameter of the adjacent non-stenotic vein must be between 5.0 and 9.0mm.
 

Exclusion Criteria	
Clinical Exclusion Criteria
 
 
1. The subject is dialyzing with an AV graft.
 
2. The target lesion has had a corresponding thrombosis treated within 7 days prior to the index procedure.
 
3. The hemodialysis access is located in the lower extremity.
 
4. The subject has an infected AV fistula or uncontrolled systemic infection.
 
5. The subject has a known uncontrolled blood coagulation/bleeding disorder.
 
6. The subject has a known allergy or hypersensitivity to contrast media which cannot be adequately pre-medicated.
 
7. The subject has a known hypersensitivity to nickel-titanium (Nitinol) or tantalum.
 
8. The subject has another medical condition, which, in the opinion of the Investigator, may cause him/her to be non-compliant with the protocol, confound the data interpretation, or is associated with a life expectancy insufficient to allow for the completion of study procedures and follow-up.
 
9. The subject is currently participating in an investigational drug or another device study that has not completed the study treatment or that clinically interferes with
 

	
the study endpoints. Note: Studies requiring extended follow-up visits for products that were investigational, but have since become commercially available, are not considered investigational studies.
 
Angiographic Exclusion Criteria
 
 
10. Additional stenotic lesions (<math>\geq 50\%</math>) in the venous outflow that are <math>> 3\text{cm}</math> from the edge of the target lesion and are not successfully treated (defined as <math>\leq 30\%</math> residual stenosis) prior to treating the target lesion.
 
11. An aneurysm or pseudoaneurysm is present within the target lesion.
 
12. The location of the target lesion would require the COVERA™ Vascular Covered Stent be deployed across the elbow joint.
 
13. The target lesion is located within a stent.
 
14. The location of the target lesion would require that the COVERA™ Vascular Covered Stent be deployed at or across the segment of fistula utilized for dialysis needle puncture (i.e., “cannulation zone”).
 
15. The location of the target lesion would require that the COVERA™ Vascular Covered Stent be placed in the central veins (subclavian, brachiocephalic, Superior Vena Cava (SVC)) or under the clavicle at the thoracic outlet.
 
16. There is incomplete expansion of an appropriately sized angioplasty balloon to its expected profile, in the operator’s judgment, during primary angioplasty at the target lesion prior to randomization.
 

Procedures:
	
All subjects will undergo a clinical evaluation at screening (prior to index procedure); treated subjects will also undergo a clinical evaluation prior to hospital discharge. A telephone screen to the subject and the dialysis center will be performed at all follow-up visits. The 6 month follow up should occur via an office visit to the investigational site in addition to the phone call to the dialysis center.

Primary Endpoints
	
Primary Effectiveness Endpoints with Hypothesis Testing
 
 
• Target Lesion Primary Patency (TLPP) through 6 months.
 
 
Primary Safety Endpoint with Hypothesis Testing
 
 
• Safety through 30 days.
 


Secondary Endpoints:
	
Key Secondary Endpoint with Hypothesis Testing
 
 
• TLPP through 12 months.
 
• Access Circuit Primary Patency (ACPP) through 6 months.
 
 
Secondary Endpoints without Hypothesis Testing
 
 
• TLPP through 30 days, 90 days, 18 months, and 24 months.
 
• ACPP through 30 days, 90 days, 12 months, 18 months, and 24 months.
 
• Rate of device and procedure related AEs involving the AV access circuit through 90 days, 6 months, 12 months, 18 months, and 24 months.
 
• Total Number of AV Access Circuit Reinterventions through 30 days, 90 days, 6 months, 12 months, 18 months, and 24 months.
 
• Total Number of Target Lesion Reinterventions through 30 days, 90 days, 6 months, 12 months, 18 months, and 24 months.
 
• Index of Patency Function (IPF) evaluated at 30 days, 90 days, 6 months, 12 months, 18 months, and 24 months.
 
• Index of Patency Function – Target Lesion (IPF-T) evaluated at 30 days, 90 days, 6 months, 12 months, 18 months, and 24 months.
 
• Secondary Patency evaluated through 30 days, 90 days, 6 months, 12 months, 18
 

---

	months, and 24 months. 

• Acute Technical Success.

• Acute Procedure Success (Anatomic and Clinical Success).

Lead Principal Investigator:	[REDACTED]
Angiographic Core Lab	[REDACTED]

---

## STATISTICAL ANALYSIS PLAN

### 1.1 Overview of Study Design

The clinical study will be a prospective, multi-center, randomized safety and effectiveness study with the primary objective to demonstrate superior effectiveness and non-inferior safety of the COVERA™ Vascular Covered Stent by direct comparison to standard PTA alone for treatment of lesions of AV fistulas.

For the study to be considered successful, superiority of the COVERA™ Vascular Covered Stent must be demonstrated for the primary effectiveness endpoint, and non-inferiority of the COVERA™ Vascular Covered Stent must be demonstrated for the primary safety endpoint as compared to PTA alone.

### 1.2 Analysis populations

The analysis populations will be defined as follows for this study:

- The ITT population will consist of all enrolled subjects who have signed the ICF and have been randomized.
- The Modified ITT (MITT) population will consist of any subjects in the ITT population who are treated with the COVERA™ Vascular Covered Stent (following PTA) or PTA alone.
- A Per-Protocol (PP) population may be created if there are subjects who have any major protocol deviations. The PP population will consist of any subjects in the MITT population who do not have any major protocol deviation. The protocol deviations that are considered to have a “major” grade will be defined a priori in the analysis plan.

All analyses including the primary analyses will be primarily based on the MITT population. PP analyses may also be performed for the primary endpoints. They will only serve as sensitivity analyses for the primary analyses which are based on the MITT population. Additionally As-treated (AT) analysis may be performed in which subjects will be analyzed based on the actual treatment received instead of the randomized treatment, if there are subjects randomized but received the wrong treatment.

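### Both primary tests use an MITT set that depends on treatment received, and no analysis is assigned to the defined ITT set; making ITT primary for the superiority tests is a cheap safeguard

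*Combined protocol and SAP*

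**What the plan says.** SAP Section 1.2 defines three sets.

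- ITT: "The ITT population will consist of all enrolled subjects who have signed the ICF and have been randomized".
- MITT: "any subjects in the ITT population who are treated with the COVERA™ Vascular Covered Stent (following PTA) or PTA alone".
- PP: an optional subset of MITT without major deviations.

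It then says: "All analyses including the primary analyses will be primarily based on the MITT population". PP analyses are optional and serve as sensitivity analyses. An As-treated analysis is also optional; in it "subjects will be analyzed based on the actual treatment received instead of the randomized treatment".

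ITT therefore appears only as the parent set of MITT. No primary, secondary, sensitivity or tipping-point analysis in the available text is assigned to it. Section 1.5 deals with missing endpoints but does not say that subjects outside MITT are brought back.

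The trial is counted in randomized subjects. The Protocol Summary (Enrollment) says: "The primary endpoint analysis will occur when 280 randomized subjects have completed or discontinued before their 6 month follow up". Section 1.6 sizes every endpoint from 280 randomized, with attrition as the only planned loss.

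**The concern.** Randomization protects a comparison only if the compared groups are the randomized ones. A set defined by treatment received can lose subjects for reasons that arise after allocation and that may differ between the arms, because one arm requires a further device step and the other does not. Success under Section 1.1 needs both primary tests to pass, and both rest on this set.

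The word *treated* is not defined. With no ITT result planned, a reader of the final report could not see whether the exclusions mattered.

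**Working it through.** **1. What the definition does.** Two readings are possible.

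- *Literal: had the index procedure, in either arm.* The definition has no condition that treatment be as assigned. The Protocol Summary describes stent after PTA, or PTA alone, and adds: "This treatment is called the “Index Procedure". Exclusion criterion 16 refers to balloon expansion "during primary angioplasty at the target lesion prior to randomization", so angioplasty has already been done when allocation occurs. A device-arm subject who gets no stent has then had PTA alone and stays in MITT. The Procedures row sets all screened subjects against those who go on to the procedure: "treated subjects will also undergo a clinical evaluation prior to hospital discharge". The As-treated sentence implies that subjects given the wrong treatment otherwise stay in MITT in their randomized arm. On this reading MITT is close to ITT; only a subject who ends with some other treatment leaves, from either arm.
- *Treated as assigned.* Device subjects without a stent and control subjects given a stent would both leave. The numbers and outcomes are not in the documents, so neither the direction nor the size of any bias is known.

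The first reading is better supported, but the text does not state it.

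**2. The plan's own power.** Inputs from Section 1.6: 6-month TLPP 73% and 50%, 280 randomized, 10% attrition, one-sided 0.025. Evaluable: 280 × 0.90 = 252, or 126 per arm. Pooled two-proportion formula, mean rate 0.615:

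- null term: 1.96 × √(2 × 0.615 × 0.385 / 126) = 0.1202
- standard error under the alternative: √((0.73 × 0.27 + 0.50 × 0.50) / 126) = 0.0596
- power: Φ((0.23 − 0.1202) / 0.0596) = Φ(1.84) = 96.7%

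With a continuity correction it is 95.6%. The stated 95% is reproduced.

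**3. What exclusions could do to the effectiveness test.** The counts are assumptions. Take a true 6-month rate of 50% in both randomized arms of 140. Drop x subjects from an arm, of whom a fraction q would have kept patency. The MITT rate in that arm is (70 − qx)/(140 − x), on 0.9 × (140 − x) evaluable. The pooled test stands in for the log-rank.

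If q = 0.50, the rate stays at 50% and the type I error at 0.025 for every x. If q = 0 (all dropped subjects fail, the extreme case):

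| Dropped | Device arm only | Control arm only |
|---|---|---|
| 1 | 0.0285 | 0.0218 |
| 2 | 0.0325 | 0.0190 |
| 3 | 0.0370 | 0.0165 |
| 5 | 0.0476 | 0.0122 |
| 7 | 0.0608 | 0.0088 |

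For example, with one device subject dropped the apparent rate is 70/139 = 50.36% against 50%. The standard error is 0.0631, the shift is 0.0036/0.0631 = 0.057, and 1 − Φ(1.96 − 0.057) = 0.0285. Equal numbers dropped give 0.0250; 5 device and 3 control give 0.0328. Counts of 1 to 2 suit the literal reading. Counts of 3 to 7 are plausible only under treated as assigned.

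**4. What ITT would cost.** Restore x device subjects to the 140, with 126 per arm evaluable as before.

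| Restored | Rate, power if restored subjects have the 50% PTA rate | Rate, power if all fail |
|---|---|---|
| 0 | 73.0%, 96.7% | 73.0%, 96.7% |
| 1 | 72.8%, 96.5% | 72.5%, 96.0% |
| 2 | 72.7%, 96.3% | 72.0%, 95.1% |
| 3 | 72.5%, 96.0% | 71.4%, 94.1% |

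The rates are (0.73 × (140 − x) + 0.50x)/140 and 0.73 × (140 − x)/140.

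**The case against.** The strongest objection is that little is wrong in practice. On the literal reading nearly every randomized subject qualifies through a step completed before allocation, the arms are still compared as randomized, and *primarily* does not bar an ITT analysis. This largely stands, and it limits the point to a safeguard. It does not supply the missing definition or commit the plan to any ITT result.

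Second, MITT has some claim to be the plan's intended basis: Section 1.6 states its assumed rates for treated subjects, and Design & Overview gives the follow-up schedule for treated subjects. That is fair. But the counts and the timing of the analysis are for randomized subjects, and the Enrollment row says all subjects are followed for 24 months. The two follow-up statements need to be aligned.

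Third, harm and cost must be judged on the same assumption. If excluded subjects do as PTA alone, there is no inflation and almost no cost; if all fail, both are visible. The tables show both cases for this reason.

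Fourth, Sections 4.1.1 to 4.2.2, to which the SAP refers for definitions, are not in the available text. The statement that nothing is assigned to ITT is limited accordingly.

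Two stronger readings are tempting.

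- A reader might infer that MITT removes device-arm failures and so favours the stent. The documents do not support this: the literal definition keeps a device subject without a stent, and under treated as assigned, control subjects given a stent would leave too.
- A reader might infer that safety should have to pass on both ITT and MITT. That would change the success criterion in Section 1.1. With three device subjects restored, safety power would fall from 92% to 83% if half have an event, or 70% if all do (enumeration of the Farrington-Manning test, 133 per arm; the plan states 91%). Nothing in the documents requires that trade.

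**Conclusion.** The point holds as a cheap improvement, not as a demonstrated bias. It is clear from Section 1.2 that both primary tests rest on a set that depends on treatment received, and that the available text gives ITT no role. On the better-supported reading the expected bias is small: none if excluded subjects do as PTA alone, and a type I error of 0.0285 to 0.0325 if 1 to 2 device subjects, all failures, are dropped. On the other reading its direction and size are unknown. All exclusion counts are assumptions, and the two-proportion test only approximates the planned log-rank test.

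**What to change.** Amend Section 1.2, and the Protocol Summary where it is affected, as follows.

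- (a) Make ITT, analysed in the randomized arm, the primary set for the superiority tests of TLPP at 6 and 12 months and ACPP at 6 months. Keep MITT, PP and As-treated as supportive.
- (b) Keep the 30-day safety non-inferiority test on MITT and add a mandatory, pre-specified ITT sensitivity analysis, with no rule that both must pass. ITT can dilute a true difference in a non-inferiority test, so it belongs beside MITT here and not in its place.
- (c) Report the ITT subjects outside MITT, by arm and with reasons.
- (d) State that *treated* means having had the index procedure in either arm, that all randomized subjects are followed, and which time zero applies to those not treated (for example the date of randomization), since the endpoints are counted from the index procedure.

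The cost is wording, plus follow-up contacts for probably a few subjects. There are no added subjects and no alpha adjustment. The downside is a slightly smaller effect estimate and the small loss of 6-month power in step 4 of the working: at most 0.7 points (96.7% to 96.0%) with three subjects restored at the PTA rate, and 2.6 points (96.7% to 94.1%) if all three fail.

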### 1.3 Randomization

The treatment randomization will be 1:1.

---

#### 1.4 Assessment of the Comparability of Treatment Groups and Poolability of Investigational Sites

To demonstrate the comparability of the Control to Test subjects, the treatment groups will be compared with respect to demographics and baseline characteristics and other covariates using t-tests or Wilcoxon nonparametric tests for means and  $\chi^2$ -tests for proportions.

Demographics, baseline characteristics and other covariates will also be compared between the treatment groups by sites using descriptive statistics. Both primary endpoints will also be summarized by treatment group and by site. This can help identify any confounding covariates that can potentially explain the variability of the treatment effect across sites. Sites with fewer than 10 treated subjects may be combined for this purpose. The pooling will be restricted within country.

For the primary effectiveness endpoint, an analysis will be performed to examine the potential for interaction of site and treatment group. A Cox regression model will be fit that includes fixed effect for treatment group, site and the interaction of treatment group and site. If the p-value for the interaction term is  $<0.15$ , it will be considered evidence of a possible significant interaction effect, and additional analyses will be performed to explore the differences between sites to assess their potential causes and whether or not they are clinically meaningful.

For the primary safety endpoint, an analysis will be performed as well to examine the potential for interaction of site and treatment group. A logistic regression model will be fit that includes fixed effect for treatment group, site and the interaction of treatment group and site. If the p-value for the interaction term is  $<0.15$ , it will be considered evidence of a possible significant interaction effect, and additional analyses will be performed to explore the differences between sites to assess their potential causes and whether or not they are clinically meaningful.

Both primary endpoints will also be presented by geography (US versus OUS). Similar analyses will be performed to examine the potential for interaction of geography and treatment group for both endpoints. A Cox regression model for the primary effectiveness endpoint and a logistic regression model for the primary safety endpoint will be fit that includes fixed effect for treatment group, geography and the interaction of treatment group and geography. If the p-value for the interaction term is  $<0.15$ , it will be considered evidence of a possible significant interaction effect, and additional analyses will be performed to explore the differences between geographies to assess their potential causes and whether or not they are clinically meaningful.

---

## 1.5 Handling of Missing Data

Study endpoints may be missing due to withdrawal of consent, Investigator's decision, LTF and subject death. It is important to minimize missing data by all means and always record the reason for missing. Missing data will be handled as described subsequently.

The primary analysis of the primary effectiveness endpoint is a survival analysis. As a sensitivity analysis, the primary safety endpoint will also be analyzed using survival analysis techniques. In survival analyses, unobserved endpoints are a standard part of the analysis; they are known as "censored observations". As long as the censoring is unrelated to the treatment, this method of handling missing endpoints produces unbiased estimates of the freedom-from-event rates. In addition, as a sensitivity analysis, the primary effectiveness endpoint will be analyzed as a proportion-based binomial rate.

For both primary endpoints, the reason for the censoring of all subjects with missing endpoints will be reported. If there is any indication that the censoring is related to the treatment group, a worst-case analysis may be performed for each primary endpoint, in addition to the standard analysis. In a worst-case analysis, an event will be assumed to have occurred at the time the subject was censored for all such subjects in the Test group. In the Control group, all subjects with missing data will be assumed *not* to have had an event.

In addition, regardless of whether missing data are related to the study intervention, a tipping-point analysis will also be performed, in which assumptions about missing data are varied from worst-case to best-case to examine at what point the missing data would alter the results of the analysis.

